5.1.3. Joint Evaluability

For subjects who have a joint injection or surgical procedure prior to the date of enrollment, the affected joints will be analyzed according to the impact of the joint injection or joint surgical procedure on the evaluability of the involved joints. See Attachment 1 for details. If a joint is considered nonevaluable at baseline, then all post-baseline joint evaluations will also be considered as nonevaluable; furthermore, this nonevaluability overrides any other documented, post baseline joint assessments. For subjects undergoing joint injections and/or procedures during the study for reasons not related to JIA, joint evaluability is summarized in Attachment 2.

For subjects undergoing a joint procedure/injection for the treatment of JIA, the corresponding joint(s) will be counted as swollen, having active arthritis, and having limited range of motion from the date of procedure onward.

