4.1. Inclusion Criteria

Each potential subject must satisfy all of the following criteria to be enrolled in the study.

- 1. Subjects must be age 2 years to less than 18 years with a body weight >15 kg at the time of screening and at Week 0.
- 2. Diagnosis must be made per JIA ILAR diagnostic criteria and the onset of disease must have been before the subject's 16th birthday.
- 3. Active JIA of one of the following subtypes:
 - a. Rheumatoid factor positive or negative pJIA for ≥3 months prior to screening, or
 - b. Systemic JIA with no systemic symptoms for ≥3 months, but with polyarthritis for >3 months prior to screening, or
 - c. Extended oligoarticular JIA ≥ 3 months prior to screening, or
 - d. Polyarticular juvenile psoriatic arthritis ≥3 months prior to screening, or,
 - e. Enthesitis-related arthritis ≥3 months prior to screening.
- 4. Failure or inadequate response to at least a 2-month course of MTX before screening.
- 5. Subjects must have ≥5 joints with active arthritis at screening and at Week 0 as defined by ACR criteria (ie, a joint with either swelling, or in the absence of swelling, limited range of motion associated with pain on motion or tenderness).
- 6. Subjects must have a screening CRP of ≥ 0.1 mg/dL with the exception of approximately 30% of the study population.

- Subjects must have active pJIA despite current use of oral, intramuscular, or subcutaneous MTX for ≥ 2 months before screening. For subjects with BSA $< 1.67 \text{ m}^2$, the MTX dose must be between 10 to 30 mg/m² per week and stable for ≥ 4 weeks before screening. For subjects with BSA $\geq 1.67 \text{ m}^2$, the MTX dose must be a minimum of 15 mg/week and must be stable for ≥ 4 weeks before screening. In situations where there is documented intolerance of doses $> 10 \text{ mg/m}^2$ weekly (for subjects with BSA $< 1.67 \text{ m}^2$) or $\geq 15 \text{ mg/week}$ (for subjects with BSA $\geq 1.67 \text{ m}^2$); or where documented country or site regulations prohibit use of $\geq 15 \text{ mg}$ of MTX per week in subjects with BSA $\geq 1.67 \text{ m}^2$, subjects may be entered into the trial on a lower dose of MTX.

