4.2. Exclusion Criteria

Any potential subject who meets any of the following criteria will be excluded from participating in the study.

Concomitant or previous medical therapies received:

- 1. Subject has initiated DMARDs and/or immunosuppressive therapy within 4 weeks prior to first study agent administration.
- 2. Subject has been treated with intra-articular, intramuscular or intravenous corticosteroids (including intramuscular corticotropin) during the 4 weeks before first study agent administration.
- 3. Subject has been treated with any therapeutic agent targeted at reducing IL-12 or IL-23, including but not limited to ustekinumab and ABT-874 within 3 months before first study agent administration.
- 4. Subject has been treated with natalizumab, efalizumab, or therapeutic agents that deplete B or T cells (eg, rituximab, alemtuzumab, or visilizumab) during the 12 months before first study agent administration, or has evidence at screening of persistent depletion of the targeted lymphocyte after receiving any of these agents.
- 5. Subject has been treated with alefacept within 3 months before first study agent administration.
- 6. Subject has been treated with abatacept within 8 weeks before first study agent administration
- 7. Subject has been treated with leflunomide within 4 weeks before first study agent administration (irrespective of undergoing a drug elimination procedure), or have received leflunomide from 4 to 12 weeks before first study agent administration and have not undergone a drug elimination procedure.
- 8. Subject has been treated with cytotoxic agents, including cyclophosphamide, nitrogen mustard, chlorambucil, or other alkylating agents.
- 9. Subject has received or is expected to receive any live viral or live bacterial vaccinations from 3 months before first study agent administration and up to 3 months after the last study agent administration.
- 10. Subject has had a BCG vaccination within 12 months of screening or is planned to receive BCG vaccination within 12 months following last study drug administration.
- 11. Subject has received IL-1ra (anakinra) within 1 week of the first study agent administration.

- 12. Subject has previously been treated with more than 2 therapeutic agents targeted at reducing TNFα, including, but not limited to, infliximab, etanercept, adalimumab, or certolizumab pegol.

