While it may be reasonable in clinical practice to identify as "nonevaluable" any joint which in the past or during study participation has been surgically altered (ie, prosthesis placement) or

medically treated (ie, intra-articular injection), the designation of "nonevaluable" for the purposes of this study is slightly different. Joints should only be designated as "nonevaluable" by the consistent joint assessor in the ePRO device if it is physically impossible to assess the joint (ie, joint inaccessible due to a cast, joint not present due to an amputation, joint deformed so as to make it impossible to assess).

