5.4.1.2. Inactive Disease

Inactive disease is indicated by the presence of all of the following:

- 1. No joints with active arthritis
- 2. No fever, rash, serositis, splenomegaly, hepatomegaly or generalized lymphadenopathy attributable to JIA
- 3. No active uveitis
- 4. Normal CRP ($\leq 0.287 \text{ mg/dL}$ for subjects without underlying inflammatory disease)
- 5. Physician Global Assessment of disease activity indicating no active disease (≤5 mm VAS)
- 6. Duration of morning stiffness <15 minutes

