ATTACHMENT

Attachment 1: Analytical considerations on joints with joint procedure/injection prior to study ^a

Procedures/Injection	Impact on Joint Count Outcome
Synovectomy	Not evaluable
Arthrodesis	Not evaluable
Joint replacement	Not evaluable
Amputation	Not evaluable
Arthrocentesis	Evaluable if happened > 3 months prior to baseline
Excision / Resection	Not evaluable
Arthrotomy	Not evaluable
Arthroscopy – surgical	Evaluable if happened > 3 months prior to baseline
	visit, otherwise not evaluable
Arthroscopy – diagnostic	Evaluable if happened > 4 weeks prior to baseline
	visit, otherwise not evaluable
Chondroplasty	Evaluable if happened > 4 weeks prior to baseline
	visit, otherwise not evaluable
Synovial cyst aspiration	Evaluable if happened > 4 weeks prior to baseline
	visit, otherwise not evaluable
Needle biopsy – synovium	Evaluable if happened > 3 months prior to baseline
	visit, otherwise not evaluable
Osteotomy	Not evaluable
Radio synovectomy	Not evaluable
Tendon surgery	Not evaluable
Bursal surgery	Not evaluable
Fracture reduction	Not evaluable
Steroid injection (IA, tendon,	Evaluable if happened > 3 months prior to baseline
sheath, bursa)	visit, otherwise not evaluable
Other injection	Not evaluable
a The joint assessors may mark a	a joint as not evaluable based on his clinical judgment, which is not

^a The joint assessors may mark a joint as not evaluable based on his clinical judgment, which is not included in this table.

Attachment 2: Analytical considerations on joints with injection and/or joint surgery for reasons NOT related to JIA during the study ^a

Procedures/Injection	Impact on Joint Count Outcome
Synovectomy	Not evaluable from procedure date onward
Arthrodesis	Not evaluable from procedure date onward
Joint replacement	Not evaluable from procedure date onward
Amputation	Not evaluable from procedure date onward
Arthrocentesis	Not evaluable from procedure date onward
Excision / Resection	Not evaluable from procedure date onward
Arthrotomy	Not evaluable from procedure date onward
Arthroscopy – surgical	Evaluable if happened > 3 months prior to evaluation, otherwise not evaluable
Arthroscopy – diagnostic	Evaluable if happened > 4 weeks prior to evaluation, otherwise not evaluable
Chondroplasty	Evaluable if happened > 4 weeks prior to evaluation, otherwise not evaluable
Synovial cyst aspiration	Evaluable if happened > 4 weeks prior to evaluation, otherwise not evaluable

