Needle biopsy – synovium	Evaluable if happened > 3 months prior to evaluation, otherwise not evaluable
Osteotomy	Not evaluable from procedure date onward
Radio synovectomy	Not evaluable from procedure date onward
Tendon surgery	Not evaluable from procedure date onward
Bursal surgery	Not evaluable from procedure date onward
Fracture reduction	Not evaluable from procedure date onward
Steroid injection (IA, tendon, sheath, bursa)	Evaluable if happened > 3 months prior to evaluation, otherwise not evaluable
Other injection	Not evaluable from procedure date onward
-	joint as not evaluable based on his clinical judgment, which is not

included in this table.

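### Joints given steroid 4 weeks to 3 months before baseline count for entry but are then ignored at every visit, which can only favour inactive disease, remission and minimal disease activity

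*SAP*

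**What the plan says.** **Entry.** Protocol 4.2, criterion 2, excludes a child treated with "intra-articular, intramuscular or intravenous corticosteroids (including intramuscular corticotropin) during the 4 weeks before first study agent administration". An intra-articular injection before those 4 weeks is no bar. Protocol 4.1, criterion 5, reads "Subjects must have ≥5 joints with active arthritis at screening and at Week 0 as defined by ACR criteria" and makes no exception for injected joints.

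**Assessment.** Protocol 9.2.1.1 says that past injection of a joint is not in itself a ground for calling it nonevaluable in this study. That label is to be given only "by the consistent joint assessor in the ePRO device if it is physically impossible to assess the joint".

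**Analysis.** The steroid-injection row of SAP Attachment 1 (procedures before the study) begins "Evaluable if happened > 3 months prior to baseline"; a more recent injection makes the joint not evaluable. SAP 5.1.3 then says "If a joint is considered nonevaluable at baseline, then all post-baseline joint evaluations will also be considered as nonevaluable", and adds that this status takes precedence over whatever is documented for the joint later. For a steroid injection given on study for reasons other than JIA, SAP Attachment 2 says "Evaluable if happened > 3 months prior to evaluation, otherwise not evaluable", so there the exclusion lapses.

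**Endpoints.** SAP 5.4.1.2 lists six criteria for inactive disease, the first being "No joints with active arthritis". SAP 5.4.1.3 builds clinical remission on medication from inactive disease. SAP 5.4.1.5 defines minimal disease activity by a swollen joint count of at most 1 together with two global ratings. None of these sections says how a nonevaluable joint is treated. The rescaling of joint counts in SAP 5.1.4 is stated for JIA ACR endpoints only.

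**The concern.** The joints removed are those recently bad enough to inject. The assessor examines them at every visit and the findings are in the database, but the SAP sets them aside. Inactive disease, remission and minimal disease activity ask what is active now and need no baseline. Removing a joint from such a count can lower it or leave it unchanged, but cannot raise it. Any error therefore runs toward a better-looking result, and in a single-arm study no comparator shares it.

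The same word, nonevaluable, also carries one meaning for the assessor in the protocol and a much wider one in the SAP, with no explanation of the difference.

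**Working it through.** The plan gives no figure on this point, so there is none to reproduce. The check traces the rules and then applies the SAP 5.1.4 formula.

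**Window.** The earliest permitted interval is 4 weeks = 28 days (Protocol 4.2). The Attachment 1 limit is 3 months, about 365.25/4 = 91.3 days. Injections from about 28 to 91 days before Week 0 are thus allowed at entry and trigger the rule. For the most recent of them, the 3 months end 91.3 − 28 = 63.3 days after Week 0, about Week 9. Protocol Table 1 schedules joint assessments after that at Weeks 12, 16, 20, 24, 28, 36, 44 and 52. At all eight the joint is still excluded, although the SAP's own 3-month period has passed for every such child.

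**Illustrative child (assumed).** Five active joints at entry, *k* of them injected inside the window. Later, only the *k* injected joints remain active.

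- SAP baseline active count = (5 − *k*)/(73 − *k*) × 73. For *k* = 1: 4/72 × 73 = 4.06.
- SAP later count = 0/(73 − *k*) × 73 = 0. Without rescaling it is also 0.

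| *k* | Entry count | SAP baseline | Assessor's later count | SAP later count | Active-joint improvement: assessor / SAP |
|---|---|---|---|---|---|
| 1 | 5 | 4.06 | 1 | 0 | 80% / 100% |
| 2 | 5 | 3.08 | 2 | 0 | 60% / 100% |
| 3 | 5 | 2.09 | 3 | 0 | 40% / 100% |
| 4 | 5 | 1.06 | 4 | 0 | 20% / 100% |
| 5 | 5 | 0 | 5 | 0 | 0% / not improved (zero baseline, SAP 5.4.1.1) |

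**Inactive disease and remission.** The joint criterion is met in every row under the SAP and in none on the assessor's record.

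**Minimal disease activity.** If the active joints are swollen, the limit of 1 is met in every row under the SAP, but only for *k* = 1 on the assessor's record.

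**Change in JADAS.** This differs, because baseline loses the same joints. For *k* = 3, the JADAS 71 joint component goes from 5 to 3 on the record (−2) and from 2 to 0 under the SAP (−2). In the opposite case, where the injected joints settle and the others stay active, it goes from 5 to 2 on the record (−3) and from 2 to 2 under the SAP (0). That error runs against the drug.

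**Missing-data rule.** The last-observation rule in SAP 5.1.2 does not restore the joint, because the joint component is not missing while other joints are assessed.

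**The case against.** Four objections deserve weight.

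1. *The joint criterion is one of six.* Inactive disease also needs no systemic features attributable to JIA, no active uveitis, normal CRP, a physician global of 5 mm or less, and short morning stiffness. The physician scoring the global still sees the injected joint. Remission needs all of this at each non-missed visit over 24 weeks. This stands. A reader might infer that such children will routinely be scored as having inactive disease; the documents show only that they can be.

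2. *A fixed joint set is proper for change from baseline.* This stands for JIA ACR and for change in JADAS, which is the planned JADAS score endpoint (SAP 5.4.2). A reader might infer that JADAS scores are biased one way; the example above shows they are not. Restoring the joints at follow-up alone would do harm there: for *k* = 3 the component would go from 2 to 3, a false worsening, when the record shows 5 to 3.

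3. *The two attachments serve different purposes.* Attachment 1 deals with joints whose baseline may be affected by the procedure, and Attachment 2 with procedures after a clean baseline. Protocol 9.2.1.1 governs what the assessor enters, and the SAP may add an analysis rule on top. This stands in part: different rules are not in themselves a contradiction. But concern about a contaminated baseline gives no reason to ignore a joint in an endpoint that uses no baseline.

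4. *The consequence is small.* There is no primary or major secondary efficacy endpoint and no testing. The one efficacy decision rule, JIA ACR 30 below 50% at Week 28, uses an endpoint for which a fixed joint set is defensible. This stands, and it limits the weight of the point without removing it.

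**Conclusion.** The point holds for three endpoints: inactive disease, clinical remission on medication and minimal disease activity. For these the SAP discards findings already collected, beyond the period it treats as relevant elsewhere, and any resulting error favours the drug. In the worked case, one to five recorded active joints become none.

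This rests on reading SAP 5.1.3 together with 5.4.1.2 and 5.4.1.5 to mean that a nonevaluable joint cannot count as active or swollen. The SAP does not say so outright. It also does not say which rule wins if such a joint is injected again for JIA on study, since 5.1.3 then counts it as active from that date.

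The effect on the reported rates cannot be computed. A reader might attach a number to it. If 5% to 20% of 120 children had a recent injection, 0.05 × 120 = 6 to 0.20 × 120 = 24 would come under the rule. That rate is an assumption with no support in the documents, and the figure counts children exposed to the rule, not children misclassified, who would probably be few. The primary PK endpoint is unaffected. The change should be made because it is cheap and the direction of error is known.

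**What to change.** - **SAP 5.1.3.** Limit the permanent baseline-nonevaluable rule to change-from-baseline endpoints (JIA ACR and change in JADAS), with the same joint set at baseline and follow-up.
- **Inactive disease, clinical remission on medication, minimal disease activity.** For procedures with a time limit in Attachment 1, use the assessor's recorded joint status at every visit after that limit (3 months or 4 weeks from the procedure) has passed. State how joints that remain nonevaluable are handled, and which rule applies if a joint is injected again for JIA on study.
- **Attachments 1 and 2.** Reconcile arthrocentesis, which has a 3-month limit in the first and is permanent in the second.
- **Terminology.** Reconcile the meaning of nonevaluable in Protocol 9.2.1.1 with its meaning in the SAP, for instance by using a separate SAP term for joints excluded by an analysis rule.
- **Optional.** Repeat JIA ACR 30 once with all assessor-evaluable joints at both baseline and follow-up.

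The cost is SAP wording and programming. No new data are needed and eligibility is unchanged. Rates of inactive disease, remission and minimal disease activity may fall slightly.

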5.1.4. Adjusted Joint Counts Rules

For subjects who have an incomplete set of evaluable joints, the joint count will be adjusted to a 69 joint count for joints with limited range of motion and 73 joint count for active joints for JIA ACR endpoints. This is done by dividing the number of affected joints by the number of evaluable joints and multiplying by 69 and 73, respectively.

5.2. Primary Efficacy Endpoint

No primary efficacy endpoint is planned.

5.3. Major Secondary Endpoints

No major secondary efficacy endpoints are planned.

5.4. Other Efficacy Variable(s)

5.4.1. Definition of other efficacy endpoints

5.4.1.1. JIA ACR Response

JIA ACR responses are composite endpoints measured by the 6 pediatric ACR categories. These are as follows:

- 1. Physician's global assessment of disease activity, (0 = No arthritis activity, 100 = Extremely arthritis activity) (0-100 mm VAS)
- 2. Parent/subject assessment of overall well-being, (0 = Very well, 100 = Very poor) (0-100 mm VAS)
- 3. Number of active joints (defined as either swelling, or in absence of swelling, limited range of motion associated with pain on motion or tenderness), (0-73)
- 4. Number of joints with limited range of motion, (0-69)
- 5. Physical function by Childhood Health Assessment Questionnaire, (0-3) (See Section 5.4.1.4 for details)
- 6. CRP (unit = mg/dL)

JIA ACR 30 response⁴ is defined as \geq 30% improvement from baseline in at least 3 of the 6 components with worsening of 30% or more in no more than 1 of the above noted components. Improvement in each of the individual components is indicated by a decrease in score.

If a subject's baseline value for a component is zero (ie, no disease activity as measured by that component), the subject should be considered as not achieving 30% improvement from baseline for that component since there is no room for improvement.

JIA ACR 50, 70 and 90 responses are similarly defined using the corresponding threshold for improvement from baseline and with worsening of 30% or more in no more than 1 of the above noted components.

5.4.1.2. Inactive Disease

Inactive disease is indicated by the presence of all of the following:

- 1. No joints with active arthritis
- 2. No fever, rash, serositis, splenomegaly, hepatomegaly or generalized lymphadenopathy attributable to JIA
- 3. No active uveitis
- 4. Normal CRP ($\leq 0.287 \text{ mg/dL}$ for subjects without underlying inflammatory disease)
- 5. Physician Global Assessment of disease activity indicating no active disease (≤5 mm VAS)
- 6. Duration of morning stiffness <15 minutes

5.4.1.3. Clinical Remission While on Medication

Clinical remission while on medication for JIA is defined as inactive disease (Section 5.4.1.2) at each non-missed visit for a period of ≥ 6 months (24 weeks) while on medication. All subjects are assumed to be on medication.

For a given visit, the determination of clinical remission while on mediation for JIA will be based on the period of 24 weeks prior to the visit. To be considered clinical remission, all the visits encompassing at least 24 weeks prior to the visit will have to meet the inactive disease criteria.

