9.2.1.2. American College of Rheumatology Pediatric Response

Parent/Subject Assessment of Overall Well-being

Parent/Subject
Assessment of Overall
Wellbeing

The Parent/Subject Assessment of Overall Well being is a 10 cm visual analog scale (VAS). Parents/subjects are to complete the VAS that asks them to consider all the ways arthritis impacts their child/themselves and then indicate how the child is doing. The anchors of the scale are "very well" to "very poor". Lower scores indicate better well being. The process for including this measure in the core set of variables for the assessment of children has been captured in the literature.⁵

Subjects who are emancipated juveniles (ages 15 to <18 years) at study entry may complete the assessments themselves. The same individual (eg, parent, caregiver, or subject) who completes the assessments at the start of the study should complete the assessments throughout the study.

Rationale: Correction of the number scale units for the Physician's Global Assessment of disease activity for inactive disease.

9.2.1.2. American College of Rheumatology Pediatric Response,

Physician's Global Assessment of dDisease aActivity indicating no active disease (<0.5 cm-5 mm)

Inactive Disease

Rationale: Correction of the number scale units for the visual analog scale (VAS) used in the Physician Global Assessment of Disease Activity.

9.2.1.3. Physician Global Assessment of Disease Activity The Physician Global Assessment of dDisease aActivity is a 10 cm 100 mm VAS.

Rationale: Clarification of the construct and ordinal scores to be used to assess functioning and task performance with the Childhood Health Assessment Questionnaire (CHAQ); correction of the number scale units for the VAS used to assess the subject's pain and overall well-being; paragraph 1 of "Parent/Subject Assessment of Overall Wellbeing" was removed from Section 9.2.1.2 and was included in Section 9.2.1.4 since this assessment is a component of the CHAQ; paragraph 3 of Section 9.2.1.4, Childhood Health Assessment Questionnaire, was deleted because it was redundant to paragraph 2 which is now part of the subsection, "Parent/Subject Assessment of Overall Wellbeing."

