9.2.1.2. American College of Rheumatology Pediatric Response

The JIA ACR 30 response criteria⁵ is defined as a 30% improvement (ie, a decrease in score) from baseline in at least 3 of the following 6 components, with worsening of 30% or more in no more than 1 of the following components:

- Physician Global Assessment of Disease Activity
- Parent/Subject Assessment of Overall Well-being
- Number of active joints (defined as either swelling, or in absence of swelling, limited range of motion associated with pain on motion or tenderness)
- Number of joints with limited range of motion
- Physical function by CHAQ
- CRP

The JIA ACR 50 response, the JIA ACR 70 response, and the JIA ACR 90 response are defined as a 50% improvement, a 70% improvement, and a 90% improvement from baseline, respectively, in at least 3 of the above 6 components, with worsening of 30% or more in no more than 1 of the above components.

Inactive Disease

Inactive disease is indicated by the presence of all of the following:

- No joints with active arthritis
- No fever, rash, serositis, splenomegaly, hepatomegaly, or generalized lymphadenopathy attributable to JIA
- No active uveitis
- Normal CRP (≤0.287 mg/dL for subjects without underlying inflammatory disease)
- Physician Global Assessment of Disease Activity indicating no active disease (<5 mm)
- Duration of morning stiffness <15 minutes

Clinical Remission While on Medication for JIA

Clinical remission while on medication for JIA is defined as inactive disease at each visit for a period of ≥ 6 months while on medication.

Physician Global Assessment of Disease Activity 9.2.1.3.

The Physician Global Assessment of Disease Activity is a 100 mm VAS. Physicians are to complete the VAS that has them assess the patient's current arthritis activity. The anchors of the scale are "no arthritis activity" to "extremely active arthritis." Lower scores indicate less disease activity. The process for including this measure in the core set of variables for the assessment of children has been captured in the literature.⁵

9.2.1.4. **Childhood Health Assessment Questionnaire**

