2. GENERAL ANALYSIS DEFINITIONS

2.1. Visit Windows

All scheduled study visits should occur within ± 3 days of the intended visit through Week 28 and ± 1 week from Week 28 through Week 244.

Unless otherwise specified, actual scheduled visits will be used for the summaries and listings over time with no visit windows applied.

For PK analyses, if a subject has an infusion more than \pm 3 days of the scheduled dosing date through Week 28, the concentration data collected between such a dosing visit and the subsequent dosing visit will be excluded from the by-visit data analyses. For the visits after Week 28, if the PK sampling time deviates more than \pm 7 days of the scheduled date, the PK concentration at this visit will be excluded from the by-visit data analyses.

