5.1.2. Data Handling Rules

No data handling rules will be applied to all individual endpoints and composite endpoints that are not dichotomous. Observed data will be summarized.

For a dichotomous composite endpoint, subjects who have completely missing data (ie, all components of the composite endpoint are missing) will be assumed to be a non-responder. When at least 1 of the components is non-missing, last observation carried forward (LOCF) will be used for imputing the components with missing data.

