5.4.2. Analysis Methods

Unless otherwise specified, the analysis population will be the full analyses set defined in Section 2.3.2.

Summaries over time will be for all visits data was collected through Week 28, 52, and 252, if the visit of the endpoint is not specified. Simple descriptive summary statistics, such as n, mean, SD, median, IQ range, minimum, and maximum for continuous variables, and counts and percentages for discrete variables will be used to summarize most data.

The following endpoints will be summarized over time.

- 1. The proportion of subjects who are JIA ACR 30, 50, 70, and 90 responders
- 2. The proportion of subjects who have inactive disease
- 3. The proportion of subjects in clinical remission on medication for pJIA
- 4. The improvement from baseline in the JIA ACR core set of components
- 5. The proportions of subjects who are JIA ACR 30, 50, 70, and 90 responders by disease subtype, and/or age through Week 52
- 6. The change from baseline in CHAQ
- 7. CRP concentrations
- 8. The change from baseline in JADAS 10, 27, and 71 scores
- 9. The proportion of subjects who achieve JADAS 10, 27, and 71 minimal disease activity

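### The SAP's cut-off for inactive disease (≤5 mm) departs from the protocol's (<5 mm), and its clinical-remission rule handles missed visits in two ways that are not reconciled

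*SAP*

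**What the plan says.** **Inactive disease.** Both documents list six criteria. Five agree. On the physician global score, protocol 9.2.1.2 has "Physician Global Assessment of Disease Activity indicating no active disease (<5 mm" and SAP 5.4.1.2 has "Physician Global Assessment of disease activity indicating no active disease (≤5 mm VAS".

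**Clinical remission.** Protocol 9.2.1.2 requires inactive disease at every visit over at least 6 months and mentions no exemption for missed visits. SAP 5.4.1.3 first says that remission "is defined as inactive disease (Section 5.4.1.2) at each non-missed visit for a period of" at least 6 months, which it sets at 24 weeks. Its second paragraph looks back 24 weeks from each visit and adds that "all the visits encompassing at least 24 weeks prior to the visit will have to meet the inactive disease criteria".

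**Missing data and visit timing.** Under SAP 5.1.2, for a dichotomous composite, "subjects who have completely missing data (ie, all components of the composite endpoint are missing) will be assumed to be a non-responder". Under SAP 2.1, "actual scheduled visits will be used for the summaries and listings over time with no visit windows applied".

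**Use.** SAP 5.4.2 lists nine efficacy summaries over time. Two depend on these definitions: the proportion with inactive disease, and "The proportion of subjects in clinical remission on medication for pJIA". SAP 5.1.1 states that there is no testing.

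**The concern.** A plan should apply the protocol's endpoint definition or say why it does not. Here the cut-off changes from strict to inclusive without comment.

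The remission rule has a different weakness. One sentence excuses missed visits, the next speaks of all visits across at least 24 weeks, and the general rule turns a wholly missing composite into non-response. Nothing says which prevails. Two competent programmers could report different remission proportions from the same data. In a single-arm study there is no control group in which such a shift would cancel, so the proportion is read at face value.

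**Working it through.** The plan gives no figure for either endpoint, so there is none to reproduce. The check compares the texts and counts visits.

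**1. Is the cut-off difference real?** The Amendment 2 log in the protocol gives its reason for touching this criterion as "Correction of the number scale units for the Physician's Global Assessment of disease activity for inactive disease". It changed <0.5 cm to <5 mm and kept the strict sign. The amended SAP (1 August 2018) postdates protocol Amendments 2 and 3, and Amendment 4 (16 December 2019) still has <5 mm. The SAP list prints both signs elsewhere (≤0.287 mg/dL for CRP, <15 minutes for stiffness), and both match the protocol.

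**2. What does the cut-off change?** Only a score of exactly 5 mm. If the scale is recorded in whole millimetres (an assumption), six scores (0 to 5) qualify under the SAP and five (0 to 4) under the protocol. One such score at any visit that counts breaks remission under the protocol but not under the SAP. Each reclassified child moves a proportion by 1/120 = 0.83 points or 1/100 = 1.0 point.

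**3. Which visits lie in the look-back?** Protocol Table 1 schedules efficacy visits at Weeks 0, 4, 8, 12, 16, 20, 24, 28, 36, 44 and 52. Remission cannot occur before Week 28: an earlier window reaches Week 0 or beyond, and inclusion criterion 5 requires at least 5 active joints at Week 0.

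| Index week | 24 weeks earlier | Visits in window | Next earlier usable visit |
|---|---|---|---|
| 28 | 4 | 7 | none (only Week 0) |
| 36 | 12 | 6 | 8 |
| 44 | 20 | 5 | 16 |
| 52 | 28 | 4 | 24 |

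**4. How far apart are the readings?** Take a child who is inactive throughout and attends the index visit. Let visits be missed independently at rate m, with m = 2%, 5% or 10% assumed, because the documents give no rate. The chance of being counted in remission is:

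| Reading | Week 52 | Week 28 |
|---|---|---|
| A. Skip every missed visit | 100 / 100 / 100% | 100 / 100 / 100% |
| B. Attended visits must span at least 24 weeks | 1 − m² = 99.96 / 99.75 / 99.0% (one fallback visit) | 1 − m = 98 / 95 / 90% |
| C. A missed visit counts as failure | (1 − m)³ = 94 / 86 / 73% | (1 − m)⁶ = 89 / 74 / 53% |

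Reading A has the opposite fault. A child who misses Weeks 28 and 36 and is inactive at Weeks 44 and 52 counts at Week 52, with 52 − 44 = 8 documented weeks, even if active at Week 24.

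**5. What does reading B cost, over all children?** A missing index visit (m = 2.0, 5.0, 10.0%) is already non-response under SAP 5.1.2. Beyond that:
- Index Weeks 36, 44 and 52, one fallback visit: m²(1 − m) = 0.04, 0.24 and 0.9%.
- Index Week 28, no fallback: m(1 − m) = 2.0, 4.8 and 9.0%.

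**6. Does it work in the extension?** SAP 5.4.2 summarises efficacy data through Week 252. The amendment logs show 16-weekly assessments (Weeks 68, 84, 100 and so on) until Amendment 4 removed them, so some such data may exist. For index Week 84, 24 weeks earlier is Week 60, without an efficacy visit; the latest earlier one is Week 52, a span of 32 weeks. For index Week 100, Week 76 has none; Week 68 again gives 32 weeks.

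**The case against.** Most of the case against concerns remission, and much of it stands.

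- A reader might infer that one attended, inactive visit is enough for 24 weeks of remission. That takes the first sentence of SAP 5.4.1.3 alone. The second paragraph asks for visits encompassing at least 24 weeks, and a single visit does not.
- A reader might infer that a child with a missing index visit can still be in remission. SAP 5.1.2 already makes a wholly missing composite a non-response.
- A reader might conclude that the visit exactly 24 weeks earlier must be attended. The SAP says at least 24 weeks. A child inactive at Weeks 24, 36, 44 and 52 who missed Week 28 has 28 documented weeks and should qualify. An exact-week rule would also leave extension visits such as Weeks 84 and 100 undefined.

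What survives is narrower: skipping missed visits and requiring all visits are both in the text, and applying SAP 5.1.2 to an intermediate missed visit would give reading C.

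On the cut-off, the signs < and ≤ are not printed reliably throughout the protocol text available here: the ALT limit for girls is <41 in the Amendment 2 log and ≤41 in section 4.1. The inactive-disease sign does read the same way in the Amendment 1 log, the Amendment 2 log and section 9.2.1.2, so a real difference is likely, but it should be confirmed. It is also fair that the cut-off leaves a programmer no doubt, since the SAP gives one value. The fault is departure from the protocol, not ambiguity.

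**Conclusion.** The point holds as a minor correction. The cut-off is wrong as written, subject to confirming the sign in the source files. It affects two of the nine efficacy summaries, and only through scores of exactly 5 mm.

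The remission rule is not absent. Its second paragraph implies that attended visits must span 24 weeks, but its first sentence can be programmed so that a child with fewer documented weeks counts, and neither is reconciled with the protocol's requirement of every visit or with SAP 5.1.2.

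The size of either effect cannot be derived: the documents give no missed-visit rate, expected remission rate or distribution of physician scores. The percentages above rest on assumed, independent missed visits and illustrate only how far the readings can diverge. No decision depends on these endpoints.

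**What to change.** **SAP 5.4.1.2.** After checking the sign in the source files, use the protocol's <5 mm.

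**SAP 5.4.1.3.** State that remission at an index visit requires all of:
- (a) the index visit attended and inactive, with a missing index visit counted as not in remission, as SAP 5.1.2 implies;
- (b) at least one attended, inactive visit at or before the scheduled week 24 weeks earlier, taking the latest such visit as the start;
- (c) inactive disease at every attended visit from that start to the index visit, skipping missed visits in between.

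Identify visits by scheduled week, in line with SAP 2.1, and not by elapsed days. With the permitted windows, visits 24 scheduled weeks apart can be 168 ± (3 + 3) = 162 to 174 days apart for index Week 28, and 168 ± (3 + 7) = 158 to 178 days for Weeks 36 to 52. A strict 168-day count would exclude children seen on schedule.

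This keeps the SAP's minimum of 24 weeks and covers extension visits.

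**Cost.** Two wording edits and derivation code, with no new data. The reported remission proportion may be slightly lower, by the amounts in step 5 of the working; the loss is largest at Week 28, where no earlier visit can stand in for a missed Week 4.
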